Appendix A.

Total Bilirubin Table for Term and Preterm Neonates

PARAMETER	GRADE 1 MILD	GRADE 2 MODERATE	GRADE 3 SEVERE	GRADE 4 POTENTIALLY LIFE- THREATENING
Total Bilirubin¹⁹, High (mg/dL; $\mu\text{mol/L}$) ²⁰				
Term Neonate²¹ < 24 hours of age	4 to < 7 68.4 to < 119.7	7 to < 10 119.7 to < 171	10 to < 17 171 to < 290.7	≥ 17 ≥ 290.7
24 to < 48 hours of age	5 to < 8 85.5 to < 136.8	8 to < 12 136.8 to < 205.2	12 to < 19 205.2 to < 324.9	≥ 19 ≥ 324.9
48 to < 72 hours of age	8.5 to < 13 145.35 to < 222.3	13 to < 15 222.3 to < 256.5	15 to < 22 256.5 to < 376.2	≥ 22 ≥ 376.2
72 hours to < 7 days of age	11 to < 16 188.1 to < 273.6	16 to < 18 273.6 to < 307.8	18 to < 24 307.8 to < 410.4	≥ 24 ≥ 410.4
7 to 28 days of age (breast feeding)	5 to < 10 85.5 to < 171	10 to < 20 171 to < 342	20 to < 25 342 to < 427.5	≥ 25 ≥ 427.5
7 to 28 days of age (not breast feeding)	1.1 to < 1.6 x ULN	1.6 to < 2.6 x ULN	2.6 to < 5.0 x ULN	≥ 5.0 x ULN
Preterm Neonate²⁰ 35 to < 37 weeks gestational age	Same as for Total Bilirubin, High, Term Neonate (based on days of age).	Same as for Total Bilirubin, High, Term Neonate (based on days of age).	Same as for Total Bilirubin, High, Term Neonate (based on days of age).	Same as for Total Bilirubin, High, Term Neonate (based on days of age).
32 to < 35 weeks gestational age and < 7 days of age	NA	NA	10 to < 14 171 to < 239.4	≥ 14 ≥ 239.4
28 to < 32 weeks gestational age and < 7 days of age	NA	NA	6 to < 10 102.6 to < 171	≥ 10 ≥ 171
< 28 weeks gestational age and < 7 days of age	NA	NA	5 to < 8 85.5 to < 136.8	≥ 8 ≥ 136.8
7 to 28 days of age (breast feeding)	5 to < 10 85.5 to < 171	10 to < 20 171 to < 342	20 to < 25 342 to < 427.5	≥ 25 ≥ 427.5
7 to 28 days of age (not breast feeding)	1.1 to < 1.6 x ULN	1.6 to < 2.6 x ULN	2.6 to < 5.0 x ULN	≥ 5.0 x ULN

¹⁹ Severity grading for total bilirubin in neonates is complex because of rapidly changing total bilirubin normal ranges in the first week of life followed by the benign phenomenon of breast milk jaundice after the first week of life. Severity grading in this appendix corresponds approximately to cut-offs for indications for phototherapy at grade 3 and for exchange transfusion at grade 4.

²⁰ A laboratory value of 1 mg/dL is equivalent to 17.1 $\mu\text{mol/L}$.

²¹ Definitions: Term is defined as ≥ 37 weeks gestational age; near-term, as ≥ 35 weeks gestational age; preterm, as < 35 weeks gestational age; and neonate, as 0 to 28 days of age.

Appendix G. Child-Pugh Score

The score employs 5 clinical measures of liver disease. Each measure is scored 1-3, with 3 indicating most severe derangement.

Measure	1 Point	2 Points	3 Points
Total bilirubin, $\mu\text{mol/L}$ (mg/dL)	<34 (≤ 2)	34-50 (2-3)	>50 (>3)
Serum albumin, g/L	>35	28-35	<28
PT INR	<1.7	1.71-2.30	>2.30
Ascites	None	Mild	Moderate to Severe
Hepatic encephalopathy	None	Grade I-II (or suppressed with medication)	Grade III-IV (or refractory)

Chronic liver disease is classified into Child-Pugh class A to C, employing the added score from above.

Points	Class
5-6	A
7-9	B
10-15	C

**LIST OF ABBREVIATIONS**

Abbreviation	Definition
AE	Adverse Event
ATC	Anatomic Therapeutic Chemical
AUC	Area Under the Curve
AUC 0-last	Area Under the Curve from time zero to last measurable plasma concentration
AUC 0-τ	Area Under the Curve during one dosing interval
AUC 0-inf	Area Under the Curve from time zero to infinity
BLQ	Below the Limit of Quantification
BMI	Body Mass Index
C last	Last measurable plasma concentration
C max	Maximum observed plasma concentration
C min	Minimum observed plasma concentration
CI	Confidence Interval
CL/F	Apparent oral clearance
CRF	Case Report Form
CV	Coefficient of Variation
ECG	ElectroCardioGram
i.e.	id est
HCV	Hepatitis C Virus
ICH	International Conference on Harmonization
IMP	Investigational Medicinal Product (synonymous with “study drug”)
IS	Included Set
$\lambda_z$	Apparent terminal elimination rate constant
LLN	Lower Limit of Normal range

Abbreviation	Definition
MedDRA ®	Medical Dictionary for Regulatory Activities ®
NCA	Non-Compartmental Analysis
PCSA	Potentially Clinically Significant Abnormalities
PK	PharmacoKinetics
PKS	PharmacoKinetic Set
PPS	Per Protocol Set
PT	Preferred Term
QRS	QRS interval duration
QT	Time interval for ventricular depolarisation and repolarisation
QTc	Corrected QT interval
QTcB	Bazett corrected QT interval
QTcF	Fridericia corrected QT interval
RAV	Resistance-Associated Variants
SAE	Serious Adverse Event
SAP	Statistical Analysis Plan
SAS ®	Statistical Analysis System ®
SD	Standard Deviation
SEM	Standard Error of the Mean
SOC	System Organ Class
SOP	Standard Operating Procedure
SVR	Sustained Virologic Response
$t_{1/2}$	Apparent terminal elimination half-life
TFLs	Tables, Figures, and Listings
$t_{last}$	Time corresponding to last measurable plasma concentration
$t_{max}$	Time to reach maximum plasma concentration

---

Abbreviation	Definition
TEAE	Treatment Emergent Adverse Event
ULN	Upper Limit of Normal range
VL	Viral load
Vz/F	Apparent volume of distribution
WBC	White Blood Cell
WHO	World Health Organisation

---

## 1. Introduction

The Statistical Analysis Plan (SAP) details the statistical methodology to be used in analyzing study data and outlines the statistical programming specifications, tables, figures and listings. It applies to the whole study on final analysis. Viral sequencing (e.g., Resistance-Associated Variants (RAV)) analyses will be described in a separate SAP.

## 2. Study objectives

### 2.1 Primary objective

The primary objective of this study is as follows:

- To evaluate the safety and tolerability of AL-335 in combination with ODV with or without SMV in subjects with GT1 or GT2 or GT3 CHC infection in treatment-naïve subjects with or without compensated Child Pugh A Cirrhosis

### 2.2 Secondary objectives

The secondary objectives of this study are as follows:

- To evaluate the efficacy of treatment with AL-335 in combination with ODV±SMV in subjects with GT1 or GT2 or GT3 CHC infection
- To evaluate the pharmacokinetics of AL-335 (and metabolites), ODV±SMV in plasma
- To evaluate the dynamics of HCV RNA in subjects with GT1 or GT2 or GT3 CHC infection treated with AL-335 in combination with ODV±SMV
- To evaluate the effect of baseline host and disease-related characteristics on treatment outcome
- To evaluate the impact of the presence of an (NS) 3 polymorphism (e.g., Q80K; SMV-containing arms only) and/or NS5A and NS5B polymorphisms at baseline on treatment outcome
- To evaluate the viral resistance profile after  $\leq 12$  weeks administration of AL-335 in combination with ODV±SMV

### 3. Study methodology

#### 3.1 Description of cohorts and groups (based on protocol version 8.1 of the 21st of December 2016)

Cohort #	GT	Cirrhosis	AL-335 dose (mg)	ODV dose (mg)	SMV dose (mg)	Duration (weeks)
1	1	N	400	50 QD	100	8
1b	1	N	800	50 QOD	--	8
2	1	N	800	50 QOD	75	8
3	1	N	800	50 QOD	75	6
4	1	N	800	50 QOD	--	8 (N=5) 12 (N=8)
5	3	N	800	50 QOD	75	8 (N=5) 12 (N=14)
6	1	Y	800	50 QOD	75	8
7	1	Y	800	25 QD	75	8
8	1	Y	800	25 QD	75	8
9	1	Y	800	25 QD	75	12
10	1	Y	800	25 QD	75	12
11	2	Y	800	25 QD	75	12
12	2	Y	800	25 QD	75	8
13-15	TBD					

Cohort #	Genotype	Cirrhosis	AL-335 dose (mg)	ODV dose (mg)	SMV dose (mg)	Duration (weeks)	Group*
1	1	No	400	50 QD	100	8	1
1b	1	No	800	50 QOD	-	8	1b+4
2	1	No	800	50 QOD	75	8	2
3	1	No	800	50 QOD	75	6	3
4	1	No	800	50 QOD	-	8 (N=5) 12 (N=8)	1b+4

5	3	No	800	50 QOD	75	8 (N=5) 12 (N=14)	5
6	1	Yes	800	50 QOD	75	8	6+7+8
7	1	Yes	800	25 QD	75	8	6+7+8
8	1	Yes	800	25 QD	75	8	6+7+8
9	1	Yes	800	25 QD	75	12	9+10
10	1	Yes	800	25 QD	75	12	9+10
11	2	Yes	800	25 QD	75	12	11
12	2	Yes	800	25 QD	75	8	12
13-15	To be determined						

\*These are combined groups for presentation purpose of all data except pharmacokinetics,

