10.7 Efficacy Analysis

Efficacy will be determined by assessing HCV RNA results by time. Where appropriate, data will be pooled if identical regimens and patient populations are evaluated in multiple cohorts. Efficacy data will be summarized in tables and by subject listings, describing percent (un)detectable. Descriptive statistics will be utilized to summarize efficacy analyses.

Viral sequencing will also be analyzed to look for evidence of emergence of resistance. Pre-treatment polymorphisms in the HCV NS3/4A, NS5A and NS5B regions, as applicable, in all subjects and relevant changes in the HCV NS3/4A, NS5A and NS5B regions, as applicable, in subjects not achieving SVR will be tabulated and described. The effect of pre-treatment NS3/4A, NS5A and NS5B polymorphisms, as applicable, on treatment outcome will be explored. These changes in viral sequence will not be regarded as AEs or SAEs. Additional exploratory characterization of the viral sequence and phenotype may be performed and will be reported accordingly.

Please refer to the statistical analysis plan for more details.

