#### 4. Statistical considerations

Efficacy and safety data will be analysed using SAS® software version 9.4 (SAS institute Inc. ██████ USA).

Pharmacokinetic data from the PK substudy will be analysed using Phoenix® WinNonLin® version 6.4 (Pharsight) and SAS® software version 9.4 (SAS Institute Inc. ██████ USA) for final analysis.

Descriptive statistics will be supplied according to the nature of the criteria:

- Quantitative variable: sample size, arithmetic mean, standard deviation (SD), standard error of the mean (SEM), minimum, median and maximum, and quartiles if necessary (with geometric mean, arithmetic and geometric coefficients of variation (CV), and quartiles for PK parameters, geometric mean will not be reported in case of value equal to 0).
- Qualitative variable: sample size, absolute and relative frequencies per class. Percentages will be provided with one decimal place.

Safety data will be organized by cohort.

All safety and pharmacokinetics listings will be sorted by cohort, subject, and measurement time if applicable.

For all except pharmacokinetics data, cohorts that evaluate the same treatment regimen for the same duration (e.g., Cohort 1b and the first 5 subjects in Cohort 4) will be pooled (using Label “Cohort 1b+Cohort 4 (8 Weeks).” If multiple treatment durations and/or regimens were assessed in a single cohort, the data for that cohort will be presented separately (e.g. Cohort 4 (12 weeks) will be separate from Cohort 4 (8 weeks), which will be pooled with cohort 1b). For cohorts with different clinical characteristics (e.g. HCV genotype, cirrhosis status),

treatment regimens or same treatment regimen but with different durations, data will be presented separately.

For pharmacokinetic data, cohorts that evaluate the same treatment regimen (including study medications and doses) in the same population (cirrhotic vs non-cirrhotic), whatever the duration, or HCV genotype will be pooled, i.e. the presentation of cohorts will be:

- Cohort 1,
- Cohort 1b+4,
- Cohort 2+Cohort 3+Cohort 5,
- Cohort 6.
- Cohort 7+Cohort 8+Cohort 9+Cohort 10+Cohort 11+Cohort 12

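### The SAP gives two conflicting groupings for all non-PK data: the Group column in 3.1 mixes ODV schedules and treatment durations that section 4 keeps apart

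*SAP*

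**What the plan says.** **SAP 3.1.** The second cohort table ends in a Group column. Its footnote says "These are combined groups for presentation purpose of all data except pharmacokinetics". In the rows below, the columns are cohort, genotype, cirrhosis, AL-335, ODV, SMV, weeks and group:

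- Cohort 6: "6 1 Yes 800 50 QOD 75 8 6+7+8"
- Cohort 7: "7 1 Yes 800 25 QD 75 8 6+7+8" (Cohort 8 has the same entries)
- Cohort 4: "4 1 No 800 50 QOD - 8 (N=5) 12 (N=8) 1b+4"

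Cohort 5, with 5 subjects at 8 weeks and 14 at 12 weeks, is a single group labelled 5.

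**SAP section 4.** For the same scope (everything except PK), the data to be pooled are from "cohorts that evaluate the same treatment regimen for the same duration". The worked example is explicit: "Cohort 4 (12 weeks) will be separate from Cohort 4 (8 weeks), which will be pooled with cohort 1b". A cohort that used more than one duration or regimen is to be shown in its parts. For cohorts that differ in clinical characteristics, the rule ends: "treatment regimens or same treatment regimen but with different durations, data will be presented separately".

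**SAP section 4, PK list.** Here a regimen is defined to include the drugs and their doses. Cohort 6 stands alone and Cohorts 7 to 12 form one pool.

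**Protocol 10.7.** For efficacy, where appropriate, "data will be pooled if identical regimens and patient populations are evaluated in multiple cohorts".

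**SAP section 6.** Extra ad hoc demographic and baseline tables are planned for all of 1b+4 (N=33) and all of Cohort 5 (N=19), because those subjects were meant to have one duration when enrolled.

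**The concern.** The 3.1 table is the only complete map from cohort to group for non-PK data, so a programmer could reasonably take column headings from it. Another programmer, starting from section 4, would build different columns for the same safety and efficacy tables. The SAP does not say which section prevails.

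Three rows are affected:

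- **6+7+8** joins two ODV schedules. The protocol (1.3) names the heart as a target organ of ODV toxicity, and safety is the primary objective, so ECG, echocardiogram and adverse event tables are where a blend would be least welcome.
- **5** would put 8-week and 12-week genotype 3 subjects in one column, although treatment was lengthened during the cohort because of early antiviral results (Protocol 1.2.1.2).
- **1b+4** would add the 8 subjects treated for 12 weeks to the 8-week subjects.

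Mixing durations also disturbs by-visit tables. In SAP 3.2 the Week 8 window is open-ended from day 54 in 8-week cohorts but closes at day 60 in 12-week cohorts. A mixed column would combine last-treatment values with mid-treatment values.

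The study is open-label and results by duration are already printed in the protocol. If the conflict stays open, the grouping will be chosen with results in view.

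**Working it through.** **1. The two specifications side by side**

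| Cohorts | SAP 3.1 Group | SAP section 4 rule applied |
|---|---|---|
| 1b, 4 | 1b+4 | 1b+4 (8 weeks); 4 (12 weeks) |
| 5 | 5 | 5 (8 weeks); 5 (12 weeks) |
| 6, 7, 8 | 6+7+8 | 6; 7+8 |
| 9, 10 | 9+10 | 9+10 |
| 1, 2, 3, 11, 12 | each alone | each alone |

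The specifications disagree in the first three rows and agree in the rest.

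**2. Interval method.** The SAP specifies two-sided 95% Clopper-Pearson intervals. For x responders out of n, the lower limit is the 2.5% quantile of Beta(x, n−x+1) and the upper limit is the 97.5% quantile of Beta(x+1, n−x). This reproduces Protocol 9.3: 18/20 gives 68.3–98.8% and 19/20 gives 75.1–99.9%, as stated there.

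**3. Inputs (Protocol Table 2-1).** Cohort 1b: 18/20 (SVR24). Cohort 4: 3/5 at 8 weeks (SVR24) and 7/8 at 12 weeks (SVR12). Cohort 5: 0/5 at 8 weeks (SVR24) and 13/14 at 12 weeks (end of treatment only). Cohort 6: 9/10 (SVR12), 11 enrolled. Cohorts 7 and 8: no results yet.

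**4. Cohort 5**

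- Section 4: 8 weeks 0/5 = 0% (0–52.2). For 12 weeks SVR is not yet known; 13/14 = 92.9% (66.1–99.8) if all 13 are sustained.
- 3.1: (0+13)/(5+14) = 13/19 = 68.4% (43.4–87.4) under the same assumption.
- Range: with 12-week SVR anywhere from 0/14 to 14/14 and 8 weeks held at 0/5, the pooled result runs from 0/19 to 14/19 = 73.7%.

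**5. Cohorts 1b and 4**

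- Section 4: 8 weeks (18+3)/(20+5) = 21/25 = 84.0% (63.9–95.5); 12 weeks 7/8 = 87.5% (47.3–99.7).
- 3.1: (21+7)/(25+8) = 28/33 = 84.8% (68.1–94.9).

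**6. Cohorts 6, 7 and 8**

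- Section 4: Cohort 6 alone is 9/10 = 90.0% (55.5–99.7); 7+8 is pending.
- 3.1: assume Cohort 6 stays at 11 and Cohorts 7 and 8 enrol 10 to 20 each. Cohort 6 is then 11/31 = 35.5% down to 11/51 = 21.6% of the group.
- If SVR in 7+8 is assumed to be 80% to 100%, and Cohort 6 enters as 9/10, the pooled rate runs from (9+32)/(10+40) = 41/50 = 82.0% to (9+40)/50 = 98.0%. These are illustrations, since no 7+8 data exist.

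**The case against.** **The outputs may never be mixed.** The 3.1 footnote speaks of presentation. Section 4 is more detailed and supplies the exact label for the 8-week pool. It organises safety data by cohort, and SVR12 is tabulated by cohort (SAP 9.2.2). The ad hoc tables in section 6 would be redundant if the main tables already pooled durations. This stands, and it makes section 4 the likely intention for 1b+4 and 5. Group 5 is also just the cohort's own number, and section 4 already tells the programmer to split it. None of this removes the conflicting map from the SAP.

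**50 mg QOD and 25 mg QD have the same average daily dose** (50/2 = 25 mg). Protocol 5.1.3 expresses QOD dosing as a daily equivalent, and 5.1.4 offers either schedule for the first cirrhotic cohort. That could be a reason for 6+7+8. The SAP does not give it, however, and its PK list separates the two schedules.

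**Stronger readings a reader might infer**

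- That the final pooled results will describe no regimen. This follows only if 3.1 drives the programming. In 1b+4 the drugs and doses are the same and the blend barely moves the estimate.
- That Protocol 10.7 forbids pooling across durations. It covers efficacy, is qualified by appropriateness, and contains neither the word only nor any mention of duration.
- That the trial is designed to compare durations. The primary objective is safety and tolerability, and no hypothesis is tested.
- That the overall SVR12 row is faulty for the same reason. The conflict between 3.1 and section 4 does not bear on it.

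**Conclusion.** The SAP contains two incompatible grouping specifications for the same non-PK outputs, and as written it is wrong in one place or the other. Section 6 points to section 4 as the intended rule for 1b+4 and 5. Nothing in either document resolves or justifies 6+7+8.

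The consequence is conditional on the 3.1 table being programmed, and its size differs by group. It is large for Cohort 5, where a pooled 68.4% would sit between 0% and 92.9%. It is small on current data for 1b+4 and unknown for 6+7+8. The Cohort 5 figure assumes that all 13 end-of-treatment responders are sustained and that the 0/5 at SVR24 also holds at SVR12. The counts also mix SVR24, SVR12 and end-of-treatment results as the protocol reports them.

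This is a point about reporting; it passes no judgement on any dose or duration.

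**What to change.** Before final programming, make the Group column in SAP 3.1 match section 4: 1; 1b+4 (8 weeks); 4 (12 weeks); 2; 3; 5 (8 weeks); 5 (12 weeks); 6; 7+8; 9+10; 11; 12. Add a sentence saying that these groups apply to all non-PK tables and figures.

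If the sponsor wants a wider pool such as 6+7+8, show it as supplementary beside its components and state the reason in the SAP.

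The cost is one table, some programming labels and a few more columns. The drawback is that several columns will be small (5, 8 and 14 subjects), with wide intervals.

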### 3.2 Visit Windows and Phase Definitions

Phases will be constructed as follows:

Trial phase	Start date	End date
Screening (phase 0)	Minimum of Date of signing the informed consent and Date of the first screening visit	1 day before the first study drug intake (AL-335+ODV( $\pm$ SMV))
Treatment (phase 1)	Date of first study drug intake (AL-335+ODV( $\pm$ SMV))	Date of last study drug intake: MAXIMUM{Date of last study drug intake (AL-335+ODV( $\pm$ SMV))} + 3 days*
Follow-up (phase 2)	End date of Treatment phase + 1	Trial termination date

\*In case the last study drug intake is missing, other dates can be used instead for date of last study drug intake: E.g. if the subject discontinued treatment (known from the disposition table): date of the withdrawal visit, if the latter is not available: date of first available FU visit minus the number of days in follow-up at which this FU visit was scheduled according to the protocol. If those dates are not available, date of trial termination.

The number of days in the treatment phase (ADY) will be defined as:

$ADY = \text{visit date} - \text{date of first study drug intake} + 1$  for visits on or after the day of first study drug intake

$ADY = \text{visit date} - \text{date of first study drug intake}$  for visits before the day of first study drug intake

In case the date of first study drug intake is missing, the date of the baseline visit can be used as date of first study drug.

Actual End of Treatment visit (EOT) is defined as the last visit in the Treatment phase.

All visits (regardless the investigated parameter) will be allocated within each phase to analysis time points based on the number of days in phase (ADY):

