4.6.2 Procedures for Subjects Who Discontinue Treatment

Subjects who discontinue from treatment should undergo the Study Completion procedures tabulated in Section 6.1 for the purpose of safety monitoring within 7 days after their last dose of study medication. Any subject that discontinues with ongoing AEs should be followed until resolution of their AE(s) or until the investigator has determined that the AE(s) has stabilized. In addition subjects should be followed up per Table 6-4 off treatment for up to 24 weeks, or when commencing therapy if earlier.

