PK Samples ⁵			X			X	X	X	X
Hematology ⁶		X	X			X	X		X
Serum Chemistries ⁶		X	X			X	X		X
Urinalysis		X	X			X	X		X
ALT/AST ⁶		X	X			X	X	X	X
HCV RNA concentrations ⁷		X	X	X	X	X	X	X	X
Plasma for drug resistance monitoring ⁸			X	X	X	X	X	X	X
Pregnancy Test ⁹		X							X
Optional stored serum sample ¹⁰		X	X			X	X	X	X

⁵ A single predose PK sample will be collected at each indicated visit for AL-335 (and metabolites), ODV and SMV concentrations for all subjects. In addition, PK samples will be collected at Week 3, 2-4 hours postdose, and at Week 4, 6-8 hours postdose. Subjects in the intensive PK subset will have the following samples collected at the Week 2 visit Predose (within 0.5 hour) and 0.5, 1, 2, 3, 4, 6, 9, and 24 hours postdose.

⁶ Blood for routine safety evaluations should be collected in a fasted state.

⁷ Plasma for HCV RNA analysis to be collected predose at Day 1, 2 and 3.

⁸ Plasma collected for HCV RNA resistance monitoring will be collected at the same time as HCV RNA quantification. The Day 1 samples must be collected predose.

⁹ A highly sensitive pregnancy test (e.g., urine or plasma) must be conducted immediately (within 4 days) prior to initiating treatment on Day 1 (local results may be used for this eligibility determination)

¹⁰ For additional safety investigations as needed.

* Weekly visit may occur ± 1 day from the expected visit date.

Table 6-4. Schedule of Events for Post-dosing (Safety and Virology) Follow-up Visits (All Treatment Cohorts)

Post-dosing Follow-up							
Assessment	Early Termination (ET) Visit ¹	Safety Follow-up Visit 4 Weeks (±1 week) After the Last Actual Dose of Study Drug	Virology Follow-up Visits (After end of Treatment ² OR After Time of Treatment Failure [if earlier]) ³				Week 24 (±2 weeks)
			Week 4 (±1 week) ⁴	Week 8 (±1 weeks)	Week 12 (±2 weeks)	Week 18 (±2 weeks)	
Physical Exam ⁵	X	X					
Echocardiogram	X	X					
Vital Signs	X	X					
Triplicate 12 Lead ECG	X	X					
Liver Ultrasound (subjects with cirrhosis)							X
Serum Chemistry w/ ALT & AST	X	X					
Hematology	X	X					
Urinalysis	X	X					
HCV RNA concentration	X	X	X	X	X	X	X
Plasma for drug resistance monitoring	X	X	X	X	X	X	X
AE & Conmed Evaluation	X	X	X	X	X	X	X
PK Samples ⁶	X	X	X	X	X	X	X

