### 6-Week Cohorts

Trial phase	Target phase day	Analysis time point (numeric version)	Analysis time point b	Time interval (days) a
Screening	$-\infty$	-1	Screening	$<0$
Treatment phase	1	0	Baseline	$\leq 1$
	2	0.2	Day 2	2
	3	0.3	Day 3	[3,5]
	7	1	Week 1	[6,11]
	14	2	Week 2	[12,18]
	21	3	Week 3	[19,25]
	28	4	Week 4	[26,32]
	35	5	Week 5	[33,39]
	42	6	Week 6	[40, $+\infty$ ]
	last visit while on study therapy or 3 days after the day of last dose	999	EOT	
Follow-up phase	25	16	Follow-up Week 4	[1,39]

	53	20	Follow-up Week 8	[40,67]
	81	24	Follow-up Week 12	[68,102]
	123	30	Follow-up Week 18	[103,144]
	165	36	Follow-up Week 24	[145, $+\infty$ ]

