**12-Week Cohorts**

Trial phase	Target phase day	Analysis time point (numeric version)	Analysis time point b	Time interval (days) a
Screening	-∞	-1	Screening	<0
Treatment phase	1	0	Baseline	≤1
	2	0.2	Day 2	2
	3	0.3	Day 3	[3,5]
	7	1	Week 1	[6,11]
	14	2	Week 2	[12,18]
	21	3	Week 3	[19,25]
	28	4	Week 4	[26,32]
	35	5	Week 5	[33,39]
	42	6	Week 6	[40,46]
	49	7	Week 7	[47,53]
	56	8	Week 8	[54,60]
	84	12	Week 12	[82, +∞]
		last visit while on study therapy or 3 days after the day of last dose	999	EOT
Follow-up phase	25	16	Follow-up Week 4	[1,39]
	53	20	Follow-up Week 8	[40,67]

	81	24	Follow-up Week 12	[68,102]
	123	30	Follow-up Week 18	[103,144]
	165	36	Follow-up Week 24	[145, +∞]

a The reference day of the Treatment and Screening phase is the day of the first study drug intake (= day 1 in Treatment phase).

b Target day in follow-up phase equals target day in the protocol minus 3 days.

If two visits fall within the same interval, the last measurement within the interval will be used for the descriptive statistics/tabulations per time point and graphics in order to have only one evaluation per subject per analysis time point. If there are two measurements on the same day and time, then the measurement with the highest sequence number will be used. Listings will include all values.

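### An early-termination visit 4 to 7 days after the last dose is filed under Follow-up Week 4 and displaced there by the 4-week safety visit, so its safety values appear in no by-time table or plot

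*SAP*

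**What the plan says.** **Phases.** SAP 3.2 ends the Treatment phase at the last study drug intake plus 3 days and starts follow-up at "End date of Treatment phase + 1". On the end-of-treatment time point it says: "Actual End of Treatment visit (EOT) is defined as the last visit in the Treatment phase". The window tables describe time point 999 in the same way: "last visit while on study therapy or 3 days after the day of last dose".

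**Allocation.** The rule is general: "All visits (regardless the investigated parameter) will be allocated within each phase to analysis time points". Follow-up Week 4 has target day 25 and interval [1,39] in the 6-week and 12-week tables. A footnote explains the offset: "Target day in follow-up phase equals target day in the protocol minus 3 days".

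**Ties.** "If two visits fall within the same interval, the last measurement within the interval will be used for the descriptive statistics/tabulations per time point". The same sentence extends this to graphics. Listings keep every value.

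**Visits.** Protocol 4.6.2 asks subjects who stop treatment to have the completion procedures "for the purpose of safety monitoring within 7 days after their last dose of study medication", and then to be followed according to Table 6-4. That table gives Early Termination its own column, to be held as soon as possible. A separate column is headed "Safety Follow-up Visit 4 Weeks (±1 week) After the Last Actual Dose of Study Drug". ECG, echocardiogram, vital signs, chemistry and haematology are marked in both columns.

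**The concern.** The protocol schedules a full safety assessment for subjects who stop early. The SAP has no time point that reliably receives it. The permitted visit period (7 days) runs past the end of the Treatment phase (3 days), and the first follow-up window is wide enough to hold both this visit and the 4-week safety visit.

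Safety is the primary endpoint, and cardiac toxicity is a named concern in the protocol. By-time summaries are planned for laboratory values (SAP 8.2), vital signs (8.3.1), ECG (8.3.2) and ejection fraction (8.3.3). On-treatment echocardiograms are sparse: Weeks 4 and 6 in 6-week groups, Weeks 4 and 8 in 8-week groups. For a subject who stops before Week 4, the early-termination echocardiogram may be the only scheduled one between screening and the safety visit. With 10 to 20 subjects per cohort, one subject is 5% to 10% of a by-time denominator.

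**Working it through.** **Inputs.** End of Treatment phase: last dose + 3 (SAP 3.2). Discontinuation visit: last dose + 0 to + 7 (protocol 4.6.2). Safety Follow-up Visit: 28 ± 7, so + 21 to + 35 (protocol Table 6-4). Follow-up Week 4: follow-up days 1 to 39 (SAP 3.2). That interval is not readable in our copy of the 8-week table; we assume [1,39] because the next 8-week window starts at day 40.

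**Step 1: reproduce the SAP's windows.** Follow-up day = days after last dose − 3, so the target for week w is 7w − 3. For weeks 4, 8, 12, 18 and 24 this gives 25, 53, 81, 123 and 165. The midpoints between neighbouring targets are (25 + 53)/2 = 39, (53 + 81)/2 = 67, (81 + 123)/2 = 102 and (123 + 165)/2 = 144. All match the SAP.

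**Step 2: place the early-termination visit.**
- + 0 to + 3: Treatment phase, so it can be EOT.
- + 4, + 5, + 6, + 7: follow-up days 1, 2, 3, 4, so Follow-up Week 4.

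Four of the eight permitted days fall outside EOT.

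**Step 3: place the safety visit.** 21 − 3 = 18 and 35 − 3 = 32. Follow-up days 18 to 32 lie wholly inside [1,39].

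**Step 4: apply the last-measurement rule.** For each early-termination day from + 4 to + 7, all 15 permitted safety-visit days (+ 21 to + 35) come later in the same window. The displacement is 4 × 15 = 60 of 60 combinations. For days + 0 to + 3 it is 0 of 60.

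**Step 5: what the tables then show.** The EOT row takes the last visit inside the Treatment phase, normally an earlier on-treatment visit, which may carry no echocardiogram. The Follow-up Week 4 row takes the safety visit. The early-termination value is in neither row. If the safety visit does not take place and no later value falls in the window, the early-termination value is shown as Follow-up Week 4, which is 25 − 4 = 21 to 25 − 1 = 24 days before that row's target.

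**Step 6: look for a rule that rescues it.** The retest rule in SAP section 4 concerns retests, not two separately scheduled visits. Substituting the withdrawal-visit date for the last-intake date applies only when the latter is missing. Neither helps.

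**The case against.** A reader might infer that the end-of-treatment and Follow-up Week 4 summaries are biased towards recovery, or that safety signals in subjects who stop for toxicity are lost. The documents support neither.

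- With target day 25, the safety visit is the right value for the Follow-up Week 4 row. That row is correct whenever the visit takes place.
- The EOT row then holds an on-treatment value, not a recovered one. No direction of bias follows.
- A value taken 4 to 7 days after the last dose is already off drug. Where an ECG, ejection-fraction or liver finding prompts the stop, protocol 7.5.2 and 7.9 provide for repeat or confirmatory measurements around that decision. These would often fall in the Treatment phase.
- Listings include all values. Worst-value tables for laboratory, vital signs and ECG use scheduled and unscheduled post-baseline measurements. Ejection-fraction declines above 5% are listed over time. There is also a maximum-decline table, which should retain the early-termination value, although the SAP does not say which measurements feed it.
- Table 6-4 asks for the visit as soon as possible, which favours the unaffected days. Four days in eight is not a probability.

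All of this stands, and it limits the point to by-time presentation. It does not give the early-termination assessment a place in those tables and plots.

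**Conclusion.** The misallocation is certain whenever an early-termination visit falls on days + 4 to + 7. Displacement is also certain if a later value of the same parameter falls in the window. The consequence is narrow: a protocol-scheduled safety assessment is missing from by-time tables and plots, or mislabelled when the safety visit is missed. The signal itself is not lost from the study.

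The number of subjects affected equals the number who stop early times the share of their visits falling on days + 4 to + 7. The documents give neither figure; the number is probably small. The conclusion rests on the last-dose date being known and on the [1,39] interval also applying to the 8-week cohorts. The correction is worth making before database lock because it is cheap and concerns how the primary endpoint is presented.

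**What to change.** In SAP 3.2, for safety parameters only:

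- Allocate visits labelled Early Termination and made no later than 7 days after the last dose to EOT (999), or to a separate Early Termination row, and exclude them from Follow-up Week 4.
- Keep Follow-up Week 4 at [1,39] for all other visits. Moving its start to day 5 would leave other visits on follow-up days 1 to 4 with no time point.
- Apply the 7-day cap strictly. Footnote 1 of protocol Table 6-4 foresees an Early Termination visit that coincides with the Safety Follow-up Visit; that visit belongs in Follow-up Week 4, not at EOT.
- Leave the virologic EOT and SVR definitions unchanged.

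The cost is a few lines of SAP text and a small programming change, with no protocol amendment. There are two minor downsides. If the EOT option is chosen, that row will contain some values taken 4 to 7 days off drug, which should be footnoted. Safety and virology will also then use slightly different EOT rules, which the SAP should state. A separate Early Termination row leaves the EOT definition as it is.
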